9.1.1 Treatment Period

Treatment Period assessments are listed in [Table 3-1](#).

The Day 1 Visit of Study 116 will be on the **same day** as the last scheduled visit of the parent study; this will occur at the Week 24 Visit for subjects from Study 113B and at the Week 8 Visit for subjects from Study 115. Subjects will NOT have to repeat any Study 116 Day 1 Visit assessments that were specified to be performed at the last scheduled visit in the parent study.

Subjects who were enrolled in Study 116, but had Day 1 study drug administration procedures delayed (e.g., due to an AE), will repeat the safety, LCI (if applicable), [REDACTED] assessments that were specified to be performed at the Day 1 Visit before receiving their first dose of study drug.

For subjects at Study 116 sites that have NOT been activated by the time the subject has completed the last scheduled visit in the parent study, the Day 1 Visit of Study 116 will NOT coincide with the last scheduled visit of the parent study. Subjects at these sites with delayed activation will have to repeat any Study 116 Day 1 assessments that were specified to be performed at the last scheduled visit in the parent study.

All subjects will have study visits on Day 1 and at Weeks 12, 24, 36, 48, 60, 72, 84, and 96.

Study Visits on Day 15 and Week 4 are only required for subjects from Study 115.

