10 STATISTICAL ANALYSIS

10.1 General Considerations

The Schedule of Assessments is provided in the clinical study protocol (CSP) Table 3-1. The precision standards for reporting safety and efficacy variables are provided in an internal Biometrics document that specifies the programming rules including the precision for derived variables.

All individual subject data for subjects who were enrolled in a parent study and who received at least 1 dose of TEZ/IVA in either parent study or in Study 116 will be presented in individual subject data listings.

Continuous variables will be summarized using the following descriptive summary statistics: the number of subjects (n), mean, standard deviation (SD), median, minimum value (min), and maximum value (max).

Categorical variables will be summarized using counts and percentages. Percentages will be presented to 1 decimal place.

Day 1, unless specified otherwise, will be defined as the day of the first dose of TEZ/IVA, in the Study 116 Part A.

Baseline value for safety analysis will be defined as the most recent non-missing measurement (scheduled or unscheduled) collected before the first dose of TEZ/IVA, whether the first dose was taken in the parent study or in Study 116 Part A. For ECGs, the baseline value will be defined as the last non-missing measurement (scheduled or unscheduled) before the first dose of TEZ/IVA or the average of measurements (triplicate) before the first dose of TEZ/IVA, whether the first dose was taken in the parent study or in Study 116 Part A.

Baseline value for efficacy analysis will be defined as the same as baseline of the parent study.

Change (absolute change) from baseline will be calculated as $\frac{\text{Post-baseline value} - \text{Baseline value}}$.

Relative change from baseline will be calculated and expressed in percentage as $\frac{100\% \times (\text{Post-baseline value} - \text{Baseline value})}{\text{Baseline value}}$.

The data from Study 116 will be integrated with data from the parent studies for the purpose of providing robust safety and efficacy analyses.

Unscheduled visits: Unscheduled visit measurements will be included in analysis as follows:

- In scheduled visit windows per specified visit windowing rules.
- In the derivation of baseline measurements.
- In the derivation of maximum/minimum values and maximum/minimum change from baseline values for safety analyses.
- In individual subject data listings as appropriate.

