12 APPENDICES

▪ Appendix A: Analysis Visit Window Mapping Rules

| Table 12-1 Visit Window Mapping Rules for Safety and Efficacy Measurements | | | | |
|-------------------------------------------------------------------------------------------|---------------------|-------------------------------------------------------------------------------------------|-------------------------|-------------------------------------|
| Assessments | Parent Study | Study 116 Visit | Target Study Day | Visit Window (in study days) |
| Safety Assessment | | | | |
| 
 • Vital Signs • Pulse Oximetry | Study 113 Part B | Baseline | -- | Defined in Section 10.1 |
| | | 116A Week 12 | 85 | [1*, 127] |
| | | 116A Week 24 | 169 | (127, 211] |
| | | 116A Week 36 | 253 | (211, 295] |
| | | 116A Week 48 | 337 | (295, 379] |
| | | 116A Week 60 | 421 | (379, 463] |
| | | 116A Week 72 | 505 | (463, 547] |
| | | 116A Week 84 | 589 | (547, 631] |
| | | 116A on Week 96 | 673 | (631, 687] |
| | | 116A Safety Follow-up | N/A | Nominal |
| | Study 115 | Baseline | -- | Defined in Section 10.1 |
| | | 116A Day 15 | 15 | [1*, 22] |
| | | 116A Week 4 | 29 | (22, 57] |
| | | 116A Week 12 | 85 | (57, 127] |
| | | 116A Week 24 | 169 | (127, 211] |
| | | 116A Week 36 | 253 | (211, 295] |
| | | 116A Week 48 | 337 | (295, 379] |
| | | 116A Week 60 | 421 | (379, 463] |
| | | 116A Week 72 | 505 | (463, 547] |
| | | 116A Week 84 | 589 | (547, 631] |
| | | 116A Week 96 | 673 | (631, 687] |
| | | 116A Safety Follow-up | N/A | Nominal |
| | | 
 • Hematology • Serum Chemistry | Study 113 Part B | Baseline |
| 116A Week 12 | 85 | | | [1*, 127] |
| 116A Week 24 | 169 | | | (127, 211] |
| 116A Week 36 | 253 | | | (211, 295] |
| 116A Week 48 | 337 | | | (295, 379] |
| 116A Week 60 | 421 | | | (379, 463] |
| 116A Week 72 | 505 | | | (463, 547] |
| 116A Week 84 | 589 | | | (547, 631] |
| 116A Week 96 | 673 | | | (631, 687] |
| 116A Safety Follow-up | N/A | | | Nominal |
| Study 115 | Baseline | | -- | Defined in Section 10.1 |
| | 116A Day 15 | | 15 | [1*, 50] |
| | 116A Week 12 | | 85 | (50, 127] |
| | 116A Week 24 | | 169 | (127, 211] |
| | 116A Week 36 | | 253 | (211, 295] |

| | | | | | |

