|----------------------------------------------------------------------------------------------------------|--------------------------------------------------------------------|--------------------------------|--------------|-------------------------|-------------------------|
| | | 116A Week 48 | 337 | (295, 379] | |
| | | 116A Week 60 | 421 | (379, 463] | |
| | | 116A Week 72 | 505 | (463, 547] | |
| | | 116A Week 84 | 589 | (547, 631] | |
| | | 116A Week 96 | 673 | (631, 687] | |
| | | 116A Safety Follow-up | N/A | Nominal | |
| 
 • ECG • Lipid Panel • Vitamin Levels | Study 113 Part B and Study 115 | Baseline | -- | Defined in Section 10.1 | |
| | | 116 Week 24 | 169 | [1*, 253] | |
| | | 116 Week 48 | 337 | (253, 421] | |
| | | 116 Week 72 | 505 | (421, 589] | |
| | | 116 Week 96 | 673 | (589, 687] | |
| | | 116A Safety Follow-up | N/A | Nominal | |
| Efficacy Assessment | | | | | |
| 
 • LCI | Study 113 Part B | Baseline | -- | Defined in Section 10.1 | |
| | | 116A Week 24 | 169 | [1*, 253] | |
| | | 116A Week 48 | 337 | (253, 421] | |
| | | 116A Week 72 | 505 | (421, 589] | |
| | | 116A Week 96 | 673 | (589, 687] | |
| | Study 115 | Baseline | -- | Defined in Section 10.1 | |
| | | 116A Day 15 | 15 | [1*, 22] | |
| | | 116A Week 4 | 29 | (22, 99] | |
| | | 116A Week 24 | 169 | (99, 253] | |
| | | 116A Week 48 | 337 | (253, 421] | |
| | | 116A Week 72 | 505 | (421, 589] | |
| | | 116A Week 96 | 673 | (589, 687] | |
| | 
 • Sweat chloride | Study 113 Part B and Study 115 | Baseline | -- | Defined in Section 10.1 |
| | | | 116A Week 24 | 169 | [1*, 253] |
| 116A Week 48 | | | 337 | (253, 505] | |
| 116A Week 96 | | | 673 | (505, 687] | |
| 
 • CFQ-R • Weight, height, BMI | Study 113 Part B | Baseline | -- | Defined in Section 10.1 | |
| | | 116A Week 12 | 85 | [1*, 127] | |
| | | 116A Week 24 | 169 | (127, 211] | |
| | | 116A Week 36 | 253 | (211, 295] | |
| | | 116A Week 48 | 337 | (295, 379] | |
| | | 116A Week 60 | 421 | (379, 463] | |
| | | 116A Week 72 | 505 | (463, 547] | |
| | | 116A Week 84 | 589 | (547, 631] | |
| | | 116A Week 96 | 673 | (631, 687] | |
| | Study 115 | Baseline | -- | Defined in Section 10.1 | |
| | | 116A Day 15 | 15 | [1*, 22] | |
| | | 116A Week 4 | 29 | (22, 57] | |
| | | 116A Week 12 | 85 | (57, 127] | |
| | | 116A Week 24 | 169 | (127, 211] | |
| | | 116A Week 36 | 253 | (211, 295] | |

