| | | 116A Week 48 | 337 | (295, 379] | |
| | | 116A Week 60 | 421 | (379, 463] | |
| | | 116A Week 96 | 673 | (631, 687] | |

| | | | | |
|--|--|--------------|-----|------------|
| | | 116A Week 72 | 505 | (463, 547] |
| | | 116A Week 84 | 589 | (547, 631] |
| | | 116A Week 96 | 673 | (631, 687] |

* Only include Day 1 post-dose measurements.

+ Weight will also be used in the threshold analysis in which the treatment baseline will be used to calculate the change; [REDACTED]

Note:

1. Visit name for analysis purpose is used to report data in tables and figures.
2. The analysis visit windows will be applied for both scheduled and unscheduled visits.
3. If no measurement is available within a visit window, the assessment will be considered missing for the visit.
4. Assessments at early treatment termination (ETT) visit will follow the windowing rules for regular visits up to 116A Week 96 if the ETT visit has a study day ≤ 687 ; otherwise, the ETT visit will be mapped into 116A Safety Follow-up (SFU) visit, if the subject doesn't have a nominal SFU visit.
5. If there is more than one measurement available within the same visit window for safety parameters, then
 - The record closest to the target day will be used.
 - If there are multiple records within the same distance from the target day, the latest record will be used.
 - SFU visit will not be windowed; instead, it will be used according to the nominal visit in relevant analyses.
6. If there is more than one measurement available within the same visit window for efficacy parameters, the record at the scheduled visit will be used. Otherwise,
 - The record closest to the target day will be used.
 - If there are multiple records within the same distance from the target day, the latest record will be used.
 - SFU visit will not be windowed; instead, it will remain as SFU.
7. [REDACTED] weight, height, and BMI assessments will be used for both efficacy and safety purposes. Their measurements will follow the visit windowing rules for efficacy parameters.

▪ **Appendix B: Standards for Safety Variable Display in TFLs**

Continuous Variables

The precision for continuous variables has been specified in the Vertex Standard Programming Rules document (Version 1.0, December 2015):

Categorical Variables: Percentages will be presented to 1 decimal place.

▪ **Appendix D: Imputation Rules for Missing Prior/Concomitant Medication Dates**

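### For Study 115 subjects, the SAP assigns Day 22 to the Day 15 window although the protocol permits only the Week 4 visit on that day, so a compliant Week 4 record can lose its place in the by-visit analyses

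*SAP*

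**What the plan says.** Protocol Table 3-1 gives the Day 15 visit a tolerance of 3 days and the Week 4 visit a tolerance of 7 days. Protocol Section 9.1.1 limits both to one parent cohort: "Study Visits on Day 15 and Week 4 are only required for subjects from Study 115".

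SAP Section 10.1 counts study days from Day 1, which "will be defined as the day of the first dose of TEZ/IVA, in the Study 116 Part A". In SAP Appendix A, Table 12-1, the Study 115 rows are:

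- Day 15, for vital signs, pulse oximetry, LCI, CFQ-R and weight/height/BMI: "116A Day 15 | 15 | [1*, 22", with Day 22 included.
- Week 4, for vital signs, pulse oximetry, CFQ-R and weight/height/BMI: "116A Week 4 | 29 | (22, 57", with Day 22 excluded and Day 57 included.
- Week 4, for LCI: "116A Week 4 | 29 | (22, 99", with Day 22 excluded and Day 99 included.

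The notes under the table settle what happens to a record:

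- Note 2: "The analysis visit windows will be applied for both scheduled and unscheduled visits".
- Note 3: "If no measurement is available within a visit window, the assessment will be considered missing for the visit".
- Note 5, for several safety records in one window: "The record closest to the target day will be used".
- Note 6, for efficacy: the scheduled-visit record is taken first, and closeness to target decides only otherwise. Note 7 puts weight, height and BMI under the efficacy rule.

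**The concern.** The windows override the visit label even for scheduled visits. A subject seen for Week 4 on the first day that the protocol allows is therefore classed by the SAP as a Day 15 observation. The site has done nothing wrong, yet the value either competes with the true Day 15 record or is reported under the wrong visit, and Week 4 is left empty.

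Week 4 is a named visit in the Study 115 MMRMs for LCI2.5, CFQ-R and BMI (SAP Sections 10.4.2.1, 10.4.2.3 and 10.4.2.4), each with an LS mean, SE, 95% CI and plot. It is also a scheduled time point in the vital-sign and pulse-oximetry summaries (SAP Sections 10.3.4 and 10.3.5). What is at stake is the correct labelling and retention of on-schedule values in those outputs.

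**Working it through.** **Inputs.** Targets are Day 15 and Day 29 (SAP Table 12-1). Tolerances are 3 and 7 days (Protocol Table 3-1). At most about 65 Study 115 subjects are potentially eligible (SAP Section 7.2).

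**Reproducing the SAP boundary.** The midpoint of adjacent targets is (15 + 29)/2 = 22. The same rule gives the other boundaries between visits: 57, 127, 211, 295, 379, 463, 547 and 631 for vital signs, pulse oximetry, CFQ-R and weight/height/BMI, and 99, 253, 421 and 589 for LCI. Each midpoint goes to the earlier visit.

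**Permitted days against windows (Study 115).**

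| Visit | Permitted days | Analysis window | Permitted days outside own window |
|---|---|---|---|
| Day 15 | 12 to 18 | 1 to 22 | none of 7 |
| Week 4 | 22 to 36 | 23 to 57 (LCI: 23 to 99) | Day 22, 1 of 15 |
| Week 12 onward | target ± 7 | as in Table 12-1 | none |

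Hematology and serum chemistry have no Week 4 visit (their Day 15 window runs to Day 50), and sweat chloride is first analysed at Week 24. These are unaffected.

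**What happens to a compliant Week 4 record on Day 22.**

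1. Safety parameters, Day 15 visit done in tolerance: that record is at most 3 days from target, against 22 − 15 = 7 for the Day 22 record. Note 5 keeps the former.
2. Efficacy parameters, Day 15 visit done: both records come from scheduled visits, so the first step of Note 6 does not separate them clearly. Whichever is chosen is reported as Day 15.
3. Day 15 visit missed: the Day 22 value is reported as Day 15.

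In all three cases Week 4 is missing under Note 3, unless another record falls in its window.

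**Day-count convention.** If Week 4 were counted as Day 28 (an assumption; the SAP uses 29), the permitted days would be 21 to 35, and Days 21 and 22 would both be affected. The conflict does not depend on the convention.

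**Size.** The documents give no visit-day distribution, so these are assumptions applied to 65 subjects.

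- Even spread over 15 days: 65 × 1/15 = 4.3 (95% range 1 to 9).
- Normal, centred on Day 29, rounded to whole days and limited to Days 22 to 36: P(Day 22) = [Φ(−6.5/SD) − Φ(−7.5/SD)] / [1 − 2Φ(−7.5/SD)].
 - SD 3: (0.0151 − 0.0062)/0.9876 = 0.9%, and 65 × 0.009 = 0.6.
 - SD 4: (0.0521 − 0.0304)/0.9392 = 2.3%, and 65 × 0.023 = 1.5.

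**The case against.** The strongest defence is that the table follows one pre-specified convention, blind to outcome: boundaries are midpoints, and ties go to the earlier visit. On this view, an exception at one boundary is a matter of taste. The convention is indeed uniform, but it does not settle Day 22. That day is 7 days from both targets, so distance favours neither visit, and the protocol permits only Week 4 on it. In the Study 115 schedules this is the only boundary that cuts into a protocol tolerance.

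The points about size stand:

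- A reader might infer that Day 22 safety values are lost. They are not. They remain in listings, in the maximum and minimum derivations (SAP Section 10.1), in the vital-sign threshold counts over the treatment-emergent period (Section 10.3.4) and in the shift to lowest oxygen saturation (Section 10.3.5).
- A reader might carry the count of about 4 into the efficacy models. The Study 115 MMRMs admit only subjects randomized to TEZ/IVA, so fewer than 65 are at risk. The documents do not give the allocation ratio. The even spread behind that count is also unsupported.
- A reader might infer that the closest-record rule removes the efficacy value. Note 6 looks first to the scheduled visit, so which record survives is unclear. What is clear is that neither can become the Week 4 value.
- Moving the boundary is not wholly free, because the windows also serve late and unscheduled records.

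**Conclusion.** The mismatch is real and follows from whole-day arithmetic: 1 of the 15 permitted Week 4 days is assigned to Day 15, and no note corrects it. Its reach is limited to the Day 15 and Week 4 by-visit summaries and to the Study 115 MMRMs for LCI2.5, CFQ-R and BMI.

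Under the assumptions above, including that every potentially eligible subject enrols, between fewer than one subject and about four are affected, with lower counts in the MMRMs. Each affected subject can lose one Week 4 value per assessment.

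The documents do not support reading this as a threat to the study's findings. The objectives concern 96 weeks of treatment, safety is summarized without testing, efficacy carries no multiplicity-controlled testing, and the later windows contain every permitted day. This is a minor correction, worth making because it is simple.

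**What to change.** In the Study 115 rows of SAP Table 12-1:

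- Close the Day 15 window at Day 21, as [1*, 21], for vital signs, pulse oximetry, LCI, CFQ-R and weight/height/BMI.
- Open Week 4 at (21, 57] for vital signs, pulse oximetry, CFQ-R and weight/height/BMI, and at (21, 99] for LCI.

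With these limits, none of the 7 permitted Day 15 days and none of the 15 permitted Week 4 days falls outside its own window. No other window changes.

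The cost is one boundary in three blocks of the table, plus a small mirror-image effect: a Day 15 visit held out of tolerance on Day 22, or an unscheduled record on that day, would be mapped to Week 4. That is a reasonable exchange, since no compliant Day 15 visit falls after Day 18.

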10.3.2 Clinical Laboratory Values

For laboratory measurements, the raw values and change from treatment baseline values of the continuous hematology, chemistry, vitamin, and lipids results will be summarized in SI units at each scheduled time point in the TE period based on the Safety Set.

The number and percentage of subjects with laboratory measurements meeting threshold criteria during the TE period will be summarized based on the Safety Set for selected laboratory measurements.

The threshold criterion shift from treatment baseline during the TE period will also be summarized for selected LFT laboratory parameters. The threshold criteria are provided in [Appendix G](#).

A listing of subjects with elevated LFT results during the TE period will be presented based on any of the following: AST $>3 \times$ ULN, ALT $>3 \times$ ULN, GGT $>3 \times$ ULN, ALP $>3 \times$ ULN, or total bilirubin $>2 \times$ ULN. For each subject in the listing, LFT assessments at all the time points will be included (scheduled and unscheduled).

In addition, a listing containing individual subject hematology and chemistry values outside the normal reference ranges will be provided. This listing will include data from both scheduled and unscheduled visits.

Only central lab results will be used for the tables. Local lab results will be included in the listings.

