| GGT | >ULN - ≤ 2.5 x ULN >2.5 - ≤ 5.0 x ULN >5.0 - ≤ 20.0 x ULN >20.0 x ULN | CTCAE grade 1-4 |

| Non-LFT Chemistry | | |
|--------------------------|----------------------------------------------------------------------------------------------------------------|-----------------------------------------------------------|
| CPK | >ULN - ≤ 2.5 x ULN >2.5 - ≤ 5 x ULN >5 - ≤ 10x ULN >10 x ULN | CTCAE grades 1-4 |
| Creatinine | >ULN - ≤ 1.5 x ULN >1.5 - ≤ 3.0 x ULN >3.0 - ≤ 6.0 x ULN >6.0 x ULN | CTCAE grades 1-4 |
| Blood Urea Nitrogen | >ULN - ≤ 1.5 x ULN >1.5 - ≤ 3.0 x ULN >3.0 - ≤ 6.0 x ULN >6.0 x ULN | Same criteria as creatinine No CTCAE |
| Sodium | Hyponatremia <LLN - ≥130 mmol/L <130 - ≥120 mmol/L <120 mmol/L | CTCAE grade 1, 3, 4 (No CTCAE grade 2) |
| | Hypernatremia >ULN - ≤ 150 mmol/L >150 mmol/L - ≤155 mmol/L >155 mmol/L - ≤ 160 mmol/L >160 mmol/L | CTCAE grade 1-4 |
| Potassium | Hypokalemia <LLN - ≥ 3.0 mmol/L <3.0 - ≥ 2.5 mmol/L <2.5 mmol/L | CTCAE grade 1&2, 3, 4 (Grade 1 and 2 are the same) |
| | Hyperkalemia >ULN - ≤ 5.5 mmol/L >5.5 - ≤ 6.0 mmol/L >6.0 - ≤ 7.0 mmol/L >7.0 mmol/L | CTCAE grade 1-4 |
| Glucose | Hypoglycemia <3.0 - ≥ 2.2 mmol/L <2.2 - ≥ 1.7 mmol/L <1.7 mmol/L | CTCAE grade 1-4 |
| | Hyperglycemia >ULN - ≤ 8.9 mmol/L >8.9 - ≤ 13.9 mmol/L >13.9 - ≤ 27.8 mmol/L >27.8 mmol/L | CTCAE grade 1-4 |
| Albumin | <35 - ≥ 30 g/L <30 - ≥ 20 g/L <20 g/L | CTCAE grade 1-3 |
| Amylase | >ULN - ≤ 1.5 x ULN >1.5 - ≤ 2.0 x ULN >2.0 - ≤ 5.0 x ULN >5.0 x ULN | CTCAE grade 1-4 |
| Lipase | >ULN - ≤ 1.5 x ULN >1.5 - ≤ 2.0 x ULN >2.0 - ≤ 5.0 x ULN >5.0 x ULN | CTCAE grade 1-4 |

| | | |
|---------------------|--------------------------------------------------------------------------------------------------------------------------------------------------------------|---------------------------------------------|
| Calcium | Hypercalcemia >ULN - ≤ 2.9 mmol/L >2.9 – ≤ 3.1 mmol/L >3.1 – ≤ 3.4 mmol/L >3.4 mmol/L | CTCAE grade 1-4 |
| | Hypocalcemia <LLN - ≥ 2.0 mmol/L <2.0 – ≥ 1.75 mmol/L <1.75 – ≥ 1.5 mmol/L <1.5 mmol/L | CTCAE grade 1-4 |
| Magnesium | Hypermagnesemia >ULN - ≤ 1.23 mmol/L >1.23 – ≤ 3.30 mmol/L >3.30 mmol/L | CTCAE grade 1, 3, 4 No CTCAE grade 2 |
| | Hypomagnesemia <LLN - ≥ 0.5 mmol/L <0.5 – ≥ 0.4 mmol/L <0.4 – ≥ 0.3 mmol/L <0.3 mmol/L | CTCAE grade 1-4 |
| Inorganic phosphate | Hypophosphatemia <0.74 – ≥ 0.6 mmol/L <0.6 – ≥ 0.3 mmol/L <0.3 mmol/L | CTCAE grade 1-4 |
| Lipid Panel | | |

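### SAP Table 12-3 labels hypoglycemia and hypophosphatemia as CTCAE grade 1-4 but gives each only three bands, so some values below the lower limit of normal may go uncounted in the threshold summary

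*SAP*

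**What the plan says.** Serum chemistry is part of the primary safety endpoint (protocol 7.1, SAP 6.1), and glucose and phosphate are both in the panel (protocol Table 11-1). Protocol 12.3.4.2 leaves the laboratory threshold criteria to the SAP, so SAP Table 12-3 is the operative definition. SAP 10.3.2 says how it is used: "The number and percentage of subjects with laboratory measurements meeting threshold criteria during the TE period will be summarized", for selected laboratory measurements in the Safety Set.

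The two rows in question are:

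- "Hypoglycemia <3.0 - ≥ 2.2 mmol/L <2.2 - ≥ 1.7 mmol/L <1.7 mmol/L", with CTCAE grade 1-4 in the Comments column
- "Hypophosphatemia <0.74 – ≥ 0.6 mmol/L <0.6 – ≥ 0.3 mmol/L <0.3 mmol/L | CTCAE grade 1-4", with the Comments entry after the bar

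A complete low-side row with the same label is calcium: "Hypocalcemia <LLN - ≥ 2.0 mmol/L <2.0 – ≥ 1.75 mmol/L <1.75 – ≥ 1.5 mmol/L <1.5 mmol/L".

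Where a row has fewer bands because a grade is absent or merged, the Comments column says so. Low sodium carries "CTCAE grade 1, 3, 4 (No CTCAE grade 2" and low potassium carries "CTCAE grade 1&2, 3, 4 (Grade 1 and 2 are the same". The glucose and phosphate rows have no such remark.

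**The concern.** Three bands cannot show four separate grades. Either a band is absent from these two rows or their label is wrong.

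If a band is absent, the likely one is the mildest, because the other low-side rows labelled grade 1-4 all open at LLN. A child whose glucose or phosphate falls below the laboratory's limit but not below the fixed starting value would then enter no low-side category, while a calcium or magnesium value just below its limit would be counted.

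If the label is wrong, a programmer or reader cannot tell which grade each of the three bands stands for.

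At stake is a count and percentage of subjects in a descriptive table for a primary-endpoint panel.

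**Working it through.** **Step 1: bands against grades.** I counted the bands in every row of Table 12-3 whose comment names CTCAE grades (from GGT onward).

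| Rows | Bands | Grades in the label | Agree? |
|---|---|---|---|
| GGT, CPK, creatinine, high sodium, high potassium, high glucose, amylase, lipase, high calcium, cholesterol, triglycerides (11 rows) | 4 | 1-4 | yes |
| Low calcium, low magnesium, low WBC, low lymphocytes, low neutrophils, low platelets (6 rows) | 4, first opens at LLN | 1-4 | yes |
| Low glucose, low phosphate (2 rows) | 3, first opens at a fixed value | 1-4 | **no** |
| Low sodium, high magnesium | 3 | 1, 3, 4; grade 2 stated as absent | yes |
| Low potassium | 3 | grades 1 and 2 stated as the same | yes |
| Albumin, low hemoglobin, high hemoglobin | 3 | 1-3 | yes |
| High lymphocytes | 2 | 2, 3 | yes |
| Leukocytosis | 1 | 3 | yes |

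Rows labelled grade 1-4: 11 + 6 + 2 = 19. Seventeen have four bands and two have three. No other row has a band count that disagrees with its own comment.

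**Step 2: which values fall in no band.** The top low-side band is 2.2 up to but not including 3.0 mmol/L for glucose, and 0.6 up to but not including 0.74 mmol/L for phosphate. A value x with 3.0 ≤ x < LLN (glucose) or 0.74 ≤ x < LLN (phosphate) is below normal but in no low-side band. For example:

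- If the glucose LLN were 3.6, the midpoint (3.6 + 3.0)/2 = 3.3 mmol/L falls in no band.
- If the phosphate LLN were 1.0, the midpoint (1.0 + 0.74)/2 = 0.87 mmol/L falls in no band.

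**Step 3: width of the uncounted range.** Width = LLN − starting value, or zero if LLN is at or below the starting value. The documents give no LLN, so the values below are assumptions.

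| Analyte | Assumed LLN (mmol/L) | Width (mmol/L) |
|---|---|---|
| Glucose | 3.3 | 3.3 − 3.0 = 0.3 |
| Glucose | 3.9 | 3.9 − 3.0 = 0.9 |
| Phosphate | 0.8 | 0.8 − 0.74 = 0.06 |
| Phosphate | 1.3 | 1.3 − 0.74 = 0.56 |

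**Step 4: whether another planned count picks these values up.** The shift summary in SAP 10.3.2 covers selected liver parameters only. The out-of-range listing shows individual values without a count. The continuous summaries describe levels and changes, not numbers of subjects below a limit. No other planned laboratory summary counts subjects with low glucose or low phosphate.

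**The case against.** Several points on the other side stand.

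- **The direction of the error is not proven.** Three bands may be intended and the label wrong, for instance with two grades merged as for potassium. The pattern of the other low-side rows makes an omitted first band more likely, but does not settle it. A line lost when the PDF was read cannot be fully excluded either, though the LLN bands of neighbouring rows came through intact.
- **A fixed starting value is not an error in itself.** Albumin, triglycerides and increased lymphocytes also start at fixed values, and triglycerides carries the grade 1-4 label with four bands. The defect is a three-band row under a four-grade label.
- **The summary covers selected measurements only.** Beyond Table 12-3, the SAP does not list which.

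A reader might also infer stronger things that the documents do not support:

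- *That these values are never reported.* Below-LLN values still reach the out-of-range listing, including those from unscheduled visits. They also enter the summaries of raw values and change from baseline at scheduled time points. Clinically significant abnormal results are reported as AEs (protocol 11.4.2 and 13.1.1.2) and so enter the AE tables.
- *That most low results would be lost.* The documents say nothing about how often mild low values occur.
- *That the report will state that no grade 1 events occurred.* The label sits in a Comments column, and the SAP does not say that grades are printed in the outputs.

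**Conclusion.** The two rows are inconsistent with their own label. That follows from the table alone and needs no assumption about laboratory limits. Because the comments on the other CTCAE-graded rows account for their bands, this is not a convention of the table.

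The under-count is conditional. It arises only if the laboratory's LLN is above 3.0 mmol/L for glucose or above 0.74 mmol/L for phosphate, and its width is then as in Step 3. The protocol itself warns, for AE grading, that pediatric reference ranges may differ from those in CTCAE (13.1.1.4). That makes the limit worth checking in subjects who were 6 to 11 years old at parent-study screening, but it does not supply the figure.

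The number of subjects affected cannot be estimated from the documents. The effect is confined to descriptive safety tables: no hypothesis test, error rate or sample size depends on it. It should be corrected because the panel belongs to the primary endpoint and the correction is cheap.

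**What to change.** First, check both rows against the CTCAE version in use. Protocol 13.1.1.4 names version 4.0 for AE grading; Table 12-3 does not name a version. Then do one of the following.

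1. **If four grades are intended:** add a first band to each row, using the central laboratory's LLN. For glucose, it covers values below LLN and at or above 3.0 mmol/L. For phosphate, it runs from below LLN down to the upper cut-off once that has been verified. Each row then has four bands for four grades and no uncovered range below LLN.
2. **If three bands are intended:** change the Comments entry to name the grades they represent, as is done for sodium and potassium, and state that milder values are excluded from the count. The uncounted range then remains, but as a stated choice.

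The cost is two table lines and, for the first option, the matching programming. Under the first option the low-glucose and low-phosphate counts may rise.
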